### **4.8.1 Dose-limiting Toxicities**

DLT data will be listed.

### **4.8.2 Adverse Events, Serious Adverse Events, and Deaths**

#### **4.8.2.1 Analyses of adverse events**

The primary focus of adverse event reporting will be on the TEAEs. A TEAE is defined as an adverse event (AE) that occurs or worsens in the period from the first dose of study drug up to 84 days after the last dose of study drug, or start of new anti-cancer therapy, whichever is earlier.

If an AE date/time of onset (occurrence, worsening, or becoming serious) is incomplete, an imputation algorithm will be used to classify the AE as pre-treatment, TEAE, or post-treatment. For example, if only the day of the AE onset is missing, the year and month will be compared with the first dose and 84 days after the last dose of study drug, or start of new anti-cancer therapy, whichever is earlier. And if the month and day of the AE onset are missing, the year will be compared with the first dose and 84 days after the last dose of study drug, or start of new anti-cancer therapy, whichever is earlier. The algorithm for imputing TEAE will be conservative and will classify an AE as a treatment emergent unless there is definitive information to determine it is non-TEAEs.

### **Analysis of all TEAE(s):**

The following TEAE summaries will be generated for the safety analysis set.

- Overview of TEAEs, summarizing number of TEAEs and number (%) of subjects with any
  - TEAE
  - Related TEAE (including possibly related, probably related, or related)
  - Any  $\geq$  grade 3 TEAE
  - Serious TEAE
  - TEAE leading to death
  - TEAE leading to permanent treatment discontinuation
  - TEAE leading to ADCT-402 delay or reduction or interruption
  - TEAE with at least one infusion related reaction
- All TEAEs by PT, showing number (%) of subjects with at least one TEAE, sorted by decreasing incidence of PTs
- All TEAEs by System Organ Class (SOC) and PT, showing number (%) of subjects with at least one TEAE, sorted by SOC in alphabetic order and decreasing incidence of PTs within SOC. This sorting order will be applied to all other AE tables, unless otherwise specified
- All TEAEs by SOC, PT and Maximum CTCAE grade
- All  $\geq$  grade 3 TEAEs by SOC, PT and Maximum CTCAE grade
- All related TEAEs by SOC, PT and Maximum CTCAE grade (including possibly related, probably related, or related)
- All Serious TEAEs by SOC and PT by SOC, PT and Maximum CTCAE grade

All AEs (including non-TEAEs), all SAEs (including non-TEAEs), all TEAEs leading to treatment discontinuation, all TEAEs leading to dose reduction, all TEAEs leading to dose delay, all TEAEs considered infusion related reactions, and all TEAEs with fatal outcome will be listed.

### 4.8.2.2 Deaths

Reasons for deaths will be summarized separately for 1) all deaths, 2) death on therapy or within 30 days after last dose of study drug.

### 4.8.3 Laboratory Data

Descriptive statistics (mean, standard deviation, median, and range) will be calculated for the raw data and for their changes from baseline at each scheduled assessment.

All results will be summarized using shift from baseline. Shifts for clinical laboratory results that can be graded according to CTCAE version 4.0 will be summarized by CTCAE grade.

Summaries by visit will include data from scheduled assessments, and all data will be reported according to the nominal visit date for which it was recorded. Unscheduled data will be included in “worst case post baseline” summaries, which will capture a worst case across all scheduled and unscheduled visits after the first dose of study treatment.

Laboratory data, including urinalysis, will be listed. Pregnancy test results will not be listed, but will be included in datasets.

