4.1.8 End of Treatment Visit

The following procedures will be performed within 30 days (+ 7 days) after study treatment discontinuation:

- Serum or urine pregnancy test.
- Physical examination including whole body skin assessment.
- Weight and vital signs.
- ECOG performance status.
- Hematology, coagulation panel, and biochemistry parameters.
- Urinalysis and sample collection for assessment of additional renal function studies.
- 12-lead ECG.
- Sample collection for central laboratory assessment of PK and ADA.
- Whole blood sample collection for central laboratory analysis of peripheral WBC populations and evaluation of CD19 and other CD markers (e.g., CD20, CD21, CD22).
- MNC) samples:
 - Whole blood (WB) sample collection with subsequent MNC isolation for retrospective central laboratory evaluation of CD19 and other CD markers (e.g., CD20, CD21, CD22).

ADCT-402-102 Protocol Amendment 3

- Collection of AE information.
- Collection of concomitant medication information.
- Bone marrow sample for disease assessment (see Section 4.1.2.1).

4.1.9 12-week Follow-up Visit

Each patient will have a sample taken for assessment of PK and ADA at 12 (± 1) weeks after their last dose of ADCT-402.

Blood Sample Collection and Adverse Event Monitoring During Long-Term Follow-up

For all patients, a PK and ADA blood sample collection will be performed 12 weeks (± 1 week) following the last dose of ADCT-402.

For all patients, collection of AEs and SAEs will continue for up to 84 days (12 weeks) after the last dose of study drug or initiation of new anti-cancer treatment (see Section 6.3.3.2).

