12.1 Appendix: Schedule of Events

The Schedule of Events for the Q3W and QW dosing schedules are shown in (Table 5 and Table 7, respectively) of this appendix. Timings for sample collections for assessment of PK, PD, and other parameters for the Q3W dosing schedule are shown in Table 6, and for the QW dosing schedule in Table 8 and Table 9.

Table 5. Schedule of Study Procedures: Every 3-Week (Q3W) Dosing

ъ .	Screening D-28 to -1			Cycle 1					Cycle 2			Cyc until P		EOT 30	12 Week Follow Up Visit	Follow- Up
Procedure	cree 28	D1	D2 ¹	D3&5 ²	D8	D15	D1	D2 ¹	D3&5 ²	D8	D15	D1	D8	(+7)days ³	(±1) week ⁴	12 (± 1) week
	ŠΩ	±3d			±2d	±2d	±3d			±2d	±2d	±3d	±2d			
Informed consent	X															
Demography	X															
Medical history ⁵	X															
Serum or urine β-HCG pregnancy test	X	X ⁶												X		
Physical examination ⁷	X	X			X	X	X			X	X	X		X		
Vital signs ⁸	X	X^9	X	X	X	X	X ⁹	X	X	X	X	X	X	X		
Height	X															
Weight	X	X			X	X	X			X	X	X		X		
ECOG performance status	X	X					X					X		X		
Bone marrow aspirate/biopsy ¹⁰	X											X ¹¹		X ¹²		
Hematology ¹³	X	X^{14}			X	X	X^{14}			X	X	X ¹⁴	X	X		
Coagulation Panel ¹⁵	X	X ¹⁴					X ¹⁴					X ¹⁴		X		
Biochemistry ¹⁶	X	X ¹⁴			X	X	X^{14}			X	X	X ¹⁴	X	X		
Urinalysis ¹⁷	X	X ¹⁴			X	X	X^{14}			X	X	X ¹⁴	X	X		
12-lead ECG	X	X^{18}	X				X^{18}	X				X ¹⁹		X		
Concomitant Medications ²⁰	X	X	X	X	X	X	X	X	X	X	X	X	X	X		
Premedication ²¹		X					X					X				
ADCT-402 Administration ²²		X					X					X				
Adverse events	X	X	X	X	X	X	X	X	X	X	X	X	X	X	X^{23}	
Survival information															X ²⁴	X ²⁴
New anti-cancer treatment information															X^{25}	X^{25}

Abbreviations: **D** = Day(s); **d** = day(s); DC = discontinue; **PD**, progressive disease; **ECG**, electrocardiogram; **ECOG**, Eastern Cooperative Oncology Group; **EOT**, end of treatment visit; β-HCG, beta-human chorionic gonadotropin.

ADC Therapeutics ADCT-402-102 Protocol Amendment 3

Refer to Table 6 for Central Lab Sample Collection Schedule.

- 1. Day 2 to occur 24 hours ($\pm 10\%$) after EOI.
- 2. Day 3 to occur 48 hours (\pm 10%) after EOI. Day 5 to occur 96 (\pm 24) hours after EOI.
- 3. After last dose of ADCT-402. EOT window is + 7 days.

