### 4.8.4 Electrocardiogram

ECG parameters (e.g. corrected QT interval [QTcF (Fridericia) or QTcB(Bazett)]) will not be converted or derived, but will be reported as provided by investigational sites.

Descriptive statistics (mean, standard deviation, median and range) for heart rate will be calculated and for their changes from baseline at each scheduled assessment.

The following abnormal QTc (including QTcF, QTcB and QTc with unspecified method) will be reported by a frequency table:

At any post-baseline with absolute value

450 - 480 ms

481 - 500 ms

$\geq$  501 ms

Change from Baseline

31 – 60 ms

>60 ms

For patients with unspecified QTc method at either baseline or post-baseline, consistent correction method is assumed within a patient, when calculating the change from baseline.

All ECG data will be listed, both for quantitative data and for overall interpretation (normal, abnormal –clinically significant, abnormal –not clinically significant) reported by investigational sites.

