#### 6.1.2 Unscheduled visits

Unscheduled visit measurements of laboratory data will be used for computation of baseline and worst values and/or grades. Re-windowing for unscheduled visits will not be performed.

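### The worst-case laboratory and any-post-baseline QTc tables have no end date, so values affected by the next anti-cancer therapy can be counted under an ADCT-402 dose level

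*SAP*

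**What the plan says.** **Laboratory.** The worst-case post-baseline summaries in SAP 4.8.3 use a window "which will capture a worst case across all scheduled and unscheduled visits after the first dose of study treatment". SAP 6.1.2 confirms what feeds them: "Unscheduled visit measurements of laboratory data will be used for computation of baseline and worst values and/or grades". Neither section gives an end date. Protocol 7.6.1.2 describes the same open window.

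**QTc.** SAP 4.8.4 tabulates absolute QTc categories under the label "At any post-baseline with absolute value", followed by categories of change from baseline, again without an end date. Protocol 7.6.1.3 applies an open worst-case window to ECGs and other safety assessments.

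**Adverse events.** SAP 4.8.2.1 closes the TEAE window: "up to 84 days after the last dose of study drug, or start of new anti-cancer therapy, whichever is earlier".

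**EOT visit.** Protocol 4.1.8 schedules it "within 30 days (+ 7 days) after study treatment discontinuation". Footnote 3 to Tables 5 and 7 counts from a different date: "After last dose of ADCT-402. EOT window is + 7 days". The visit includes "Hematology, coagulation panel, and biochemistry parameters" and a 12-lead ECG. Neither place relates the visit to the start of another therapy.

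**Layout.** SAP 4 uses all available data and tabulates by dose level. Sparse dose levels may be merged into dose ranges. SAP 4.7.2 lists the start date of subsequent therapy but does not use it to limit any laboratory or ECG summary.

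**The concern.** These patients have relapsed or refractory leukemia, and some may go on to another therapy soon after stopping ADCT-402. Suppose one of them starts that therapy and then has the EOT bloods. A low count, raised liver enzyme or long QTc caused by the new drug enters the worst-grade or outlier row of the ADCT-402 dose level. An adverse event starting on the same day is left out of the TEAE tables. The SAP thus has an attribution boundary for one safety display and none for another, and it gives no reason for the difference.

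This matters because SAP 3.3 reports that the trial stopped before dose escalation was complete. Efficacy (SAP 4.9) and DLTs (SAP 4.8.1) are now only listed, so the summary safety tables carry much of the report, and a dose level may hold only a few patients.

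**Working it through.** No figure in the plan sizes this problem. The only design calculation, in Protocol 7.3, reproduces (1 − 0.85^10 = 0.803, against the stated 80%) but has no bearing here.

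**Step 1: compare the windows.**

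| Summary | Opens | Closes |
|---|---|---|
| TEAEs (SAP 4.8.2.1) | First dose | Earlier of day 84 after last dose and new anti-cancer therapy |
| Worst-case laboratory (SAP 4.8.3, 6.1.2) | After first dose | Not stated |
| QTc categories (SAP 4.8.4) | Post-baseline | Not stated |
| By-visit laboratory, ECG and vital signs (SAP 4.8.3 to 4.8.5) | Each scheduled visit | EOT has its own row |
| ECOG shift (SAP 4.8.6) | Not stated | Not stated |

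The gap is in the second and third rows. In a by-visit table an EOT value cannot overwrite an on-treatment visit.

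**Step 2: which values can fall in the gap.** Tables 5 and 7 schedule no safety laboratory test or ECG after EOT. Exposure is therefore one scheduled visit per patient, plus unscheduled tests.

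**Step 3: how far EOT can follow new therapy.** Count days from the last dose, as in footnote 3. If new therapy starts on day s (an assumption), the overlap is 30 − s for an EOT visit on day 30, or 37 − s on day 37.

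| s (assumed) | EOT day 30 | EOT day 37 |
|---|---|---|
| 7 | 23 days | 30 days |
| 14 | 16 days | 23 days |
| 21 | 9 days | 16 days |
| 28 | 2 days | 9 days |

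With the TEAE cut-off applied, the overlap is 0 in every cell. Without it, unscheduled tests have no limit.

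**Step 4: largest effect of one patient.** Under the 3+3 design and the cap in Protocol 3.2, cohorts of 3, 6 and 10 are natural sizes. One patient is 100/3 = 33.3, 100/6 = 16.7 or 100/10 = 10 percentage points. These are upper bounds. The later value must be worse than the patient's on-treatment worst and must cross a tabulated category.

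**Step 5: illustration of the tabulated rate.** Let r be the true on-drug rate of a Grade 3 or higher worst value, f the share of patients tested after new therapy starts, and q the chance that such a test shows Grade 3 or higher because of that therapy. If these are independent, the tabulated rate is r + (1 − r)·f·q. All inputs are assumptions.

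| r | f = 0 | f = 10%, q = 30% | f = 50%, q = 80% |
|---|---|---|---|
| 10% | 10% | 12.7% | 46.0% |
| 30% | 30% | 32.1% | 58.0% |
| 50% | 50% | 51.5% | 70.0% |

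Two features matter. With f = 0 there is no bias. The largest addition in the table falls from 36 to 28 to 20 points as r rises, because a patient who already has a high grade cannot be moved.

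**The case against.** Several points on the other side stand.

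- **Frequency is unknown.** A reader might infer that the next therapy's toxicity is in fact charged to ADCT-402. The documents support only that it can be. They give no share of patients who start new therapy before EOT, so any percentage is an assumption. Protocol 4.1.8 also permits an EOT visit soon after stopping. Tables 5 and 7 collect new-therapy information only from the 12-week visit, which suggests that EOT was expected to come first, though no rule says so.
- **Ceiling.** Protocol 3.3.1 sets no minimum neutrophil or platelet count, and Protocol 5.4 gives the first two cycles whatever the blood counts. Many patients may already have high-grade cytopenia on treatment, and a later nadir would then change nothing.
- **Scope.** A reader might extend the point to vital signs and ECOG. SAP 4.8.5 summarizes vital signs by scheduled visit only. SAP 4.8.6 states no worst-value rule, so it cannot be said to take every value.
- **What is untouched.** A reader might infer that the primary safety result is compromised. DLTs, with their one-cycle observation period, and the TEAE tables are not affected. Some difference between laboratory and TEAE tables is also expected, since Protocol 6.3.5 makes only clinically significant abnormalities adverse events.
- **Traceability.** Laboratory data, ECG data and therapy start dates are all listed, so an affected value can be found by hand. That helps, but it does not correct the summary table.

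One reply does not stand. Protocol 5.9.1 prohibits other anti-cancer therapy during the study, but Protocol 4.1.10 and 6.3.3.2 expect new therapy after discontinuation, and 6.3.3.2 refers to it in limiting AE collection. The prohibition does not keep EOT values free of it.

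**Conclusion.** The point holds for two displays: the worst-case laboratory summaries (including any shift table built on the worst grade) and the QTc outlier table. Followed as written, SAP 4.8.3 and 4.8.4 can count values affected by a later therapy under an ADCT-402 dose level, while SAP 4.8.2.1 excludes adverse events starting in the same period.

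The number of affected patients cannot be derived from the documents. The per-patient effect is at most 33, 17 or 10 points for n = 3, 6 or 10, subject to the two conditions in Step 4, and smaller if dose levels are merged. The rates in Step 5 show direction and range only.

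A reader might also infer that the bias is greatest at dose levels where patients stop earliest, or that the two EOT anchor dates cause the problem. Nothing in the documents establishes the first. On the second, the mismatch between Protocol 4.1.8 and footnote 3 is real and should be reconciled, but it is separate and secondary: with either anchor the SAP tables would still lack an end date.

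This is a modest but worthwhile correction to a descriptive analysis, because the SAP already contains the boundary it needs.

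**What to change.** Add one sentence to SAP 4.8.3 and 4.8.4: worst-case post-baseline laboratory summaries (including worst-grade shifts) and QTc outlier categories, absolute and change from baseline, use only values up to the end of the TEAE window defined in 4.8.2.1; later values are listed and flagged. If the ECOG shift in 4.8.6 uses a worst post-baseline value, say so and apply the same limit. By-visit summaries need no change.

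The cost is that sentence and one date filter. No new data are needed: the protocol has subsequent therapy recorded in the eCRF (Tables 5 and 7, footnote 25), and SAP 4.7.2 already lists its start date. The downside is that a few EOT or unscheduled values move from tables to listings. Since the trial has ended early, changing the protocol's EOT timing would achieve little now; the SAP change is the useful one.

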### 4.8.4 Electrocardiogram

ECG parameters (e.g. corrected QT interval [QTcF (Fridericia) or QTcB(Bazett)]) will not be converted or derived, but will be reported as provided by investigational sites.

Descriptive statistics (mean, standard deviation, median and range) for heart rate will be calculated and for their changes from baseline at each scheduled assessment.

The following abnormal QTc (including QTcF, QTcB and QTc with unspecified method) will be reported by a frequency table:

At any post-baseline with absolute value

450 - 480 ms

481 - 500 ms

$\geq$  501 ms

Change from Baseline

31 – 60 ms

>60 ms

For patients with unspecified QTc method at either baseline or post-baseline, consistent correction method is assumed within a patient, when calculating the change from baseline.

All ECG data will be listed, both for quantitative data and for overall interpretation (normal, abnormal –clinically significant, abnormal –not clinically significant) reported by investigational sites.

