6.3.6 Electrocardiograms

A 12-lead ECG is to be performed at the time points identified in the Schedule of Events for the Q3W and QW dosing schedules (Table 5 and Table 7, respectively) in Appendix 12.1. Any abnormalities, including those that worsen from baseline, believed to be clinically significant in the medical and scientific judgment of the Investigator are to be recorded as AEs or SAEs.

Measurement of the QTc interval may be obtained according to the formula used by the institution, however, the Fridericia formula is preferred (Fridericia, 1920). The same formula used to confirm eligibility must be applied within a patient for the duration of the study.

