## 4 Statistical methods

All analyses use SAS® version 9.4 or higher. Summary tables will be organized by each dose level; if some dose levels have only a few subjects, then dose levels can be combined into dose ranges. All available data will be used in the analyses, and important data will be included in data listings, sorted by dose level, subject, and by visit within subject. Missing data will not be imputed, except via censoring in survival analyses and as otherwise specified.

Unless otherwise noted, categorical data will be presented using counts and percentages, with the number of subjects in the analysis set by treatment group as the denominator for percentages. Percentages will be rounded to one decimal place, except 100% will be displayed without any decimal places, and percentages will not be displayed for zero counts. Continuous data, unless otherwise noted, will be summarized using the number of observations (n), mean, standard deviation (std), median, minimum, and maximum. Minima and maxima will be rounded to the precision of the original value, and means, medians, and confidence intervals (CIs) if presented will be rounded to 1 decimal place greater than the precision of the original value. The std will be rounded to 2 decimal places greater than the precision of the original value, up to a maximum of 3 decimal places.

No hypothesis testing will be performed in this study.

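### SAP 4.8.4 puts QTcF, QTcB and unspecified-method QTc into one outlier table with common cut-offs and no stated split by method, so any Bazett values are binned partly by heart rate

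*SAP*

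**What the plan says.** Protocol 6.3.6 leaves the choice of formula to the site: "Measurement of the QTc interval may be obtained according to the formula used by the institution"; "however, the Fridericia formula is preferred". Within a patient, the formula used to confirm eligibility must be kept throughout. Nothing requires the same formula across patients or sites.

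SAP 4.8.4 takes the readings as they come. ECG parameters "will not be converted or derived, but will be reported as provided by investigational sites". The outlier table is then defined: "The following abnormal QTc (including QTcF, QTcB and QTc with unspecified method) will be reported by a frequency table". It has one set of absolute rows (450-480, 481-500 and ≥501 ms, at any post-baseline assessment) and one set of change rows (31-60 and >60 ms). Where the method is unspecified at either time point, "consistent correction method is assumed within a patient, when calculating the change from baseline". No split by method is stated.

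The other planned ECG outputs are a heart-rate summary ("Descriptive statistics (mean, standard deviation, median and range) for heart rate will be calculated") and listings ("All ECG data will be listed, both for quantitative data and for overall interpretation"). The outlier table is therefore the only aggregate summary of QTc that the SAP specifies.

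SAP 3.3 records that the trial ended before dose escalation was complete, so only Part 1 is analysed. SAP 4 presents tables by dose level.

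**The concern.** The two named corrections agree only at 60 bpm. Above that Bazett reads higher than Fridericia, and below it Bazett reads lower. Applying the same millisecond limits to both puts patients on different scales into the same rows. Within a patient measured by Bazett throughout, a change in heart rate between baseline and a later ECG appears as a change in QTc.

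The protocol's same-formula rule and the SAP's consistent-method assumption deal with formula switching inside a patient. Neither deals with mixed scales between patients, nor with heart-rate drift in a Bazett patient.

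At stake is the reading of a safety table in a study whose primary objective is safety and tolerability. If Bazett values are present, the table alone cannot tell QT prolongation from a heart-rate change. The absolute rows count any post-baseline value, so a single ECG at a raised heart rate can be enough to place a patient in a row.

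**Working it through.** **Inputs.** The cut-offs come from SAP 4.8.4. The entry limit comes from Protocol 3.3.2, exclusion criterion 17: a QTc of 450 ms or more at Screening excludes, with exceptions for pacemaker and bundle branch block. The documents give no heart rates, no QTcF values and no share of Bazett readings. Every heart rate and QTcF value below is an assumption. The plan states no figure to reproduce.

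**Formula.** With RR = 60/HR, QTcB = QT/RR^(1/2) and QTcF = QT/RR^(1/3). Hence QTcB/QTcF = (HR/60)^(1/6).

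| HR (bpm) | 50 | 60 | 65 | 70 | 90 | 100 | 103 | 105 | 110 |
|---|---|---|---|---|---|---|---|---|---|
| Ratio | 0.9701 | 1.0000 | 1.0134 | 1.0260 | 1.0699 | 1.0889 | 1.0942 | 1.0978 | 1.1063 |

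**Over-count, QTcF constant** (results from unrounded ratios)

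- QTcF 414: 414 × 1.0260 = 424.8 at 70 bpm; 414 × 1.0889 = 450.8 at 100 bpm. Enters 450-480.
- QTcF 410, 70 to 110 bpm: 410 × (1.1063 − 1.0260) = +32.9 ms. Enters 31-60 (and reads 453.6, so also 450-480).
- QTcF 440: 440 × 1.0134 = 445.9 at 65 bpm, below the entry limit; 440 × 1.0942 = 481.5 at 103 bpm, a change of +35.6 ms. Enters 481-500 and 31-60.
- QTcF 435: 446.3 at 70 bpm and 481.2 at 110 bpm, a change of +34.9 ms. Enters the same two rows.

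**Over-count, with a true rise.** QTcF goes from 420 to 445 (+25 ms, no row on the QTcF scale) while heart rate goes from 65 to 105 bpm. Bazett reads 420 × 1.0134 = 425.6, then 445 × 1.0978 = 488.5, a change of +62.9 ms. Enters 481-500 and >60.

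**Under-count.** QTcF goes from 400 to 435 (+35 ms) while heart rate falls from 90 to 70 bpm. Bazett reads 428.0, then 446.3, a change of +18.4 ms. No row is entered. At 50 bpm, QTcB reaches 450 only when QTcF is 450/0.9701 = 463.9 ms.

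**How far heart rate alone can go.** For constant QTcF q, an absolute target T is reached at HR = 60 × (T/q)^6. For the change rows, T is the baseline QTcB plus 31 or 60 ms.

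| q (ms), baseline HR | 450 | 481 | 501 | +31 | >60 |
|---|---|---|---|---|---|
| 410, 70 bpm | 105 | 156 | 200 | 107 | 156 |
| 435, 70 bpm | 74 | 110 | 140 | 105 | 149 |
| 440, 65 bpm | 69 | 102 | 131 | 97 | 139 |

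The entries are heart rates in bpm. The lower rows are reached at about 70 to 110 bpm in most cells. The ≥501 and >60 rows need 131 bpm or more in these three scenarios. That is not a floor. A patient right at the entry limit, with QTcF 449 and a baseline heart rate of 60 bpm, would reach 501 at 60 × (501/449)^6 = 116 bpm.

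**The case against.** The strongest reply has four parts.

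1. **The SAP is open about what it does.** It names the three types, says values are reported as received and states its assumption for unlabelled readings. Table shells are not among the documents, and the parenthesis could be programmed as separate rows. This stands in part. A reader might infer that the plan has decided to pool the methods within a row; the text does not say so, and a split is neither required nor excluded. But following the text as written produces mixed-scale counts, and one sentence would settle it.

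2. **The context is small.** Only Part 1 of an early-terminated trial is analysed, there is no hypothesis testing, and no rule depends on this table. With small dose groups the ECG listing can be read patient by patient. Clinically significant ECG abnormalities are recorded as AEs or SAEs. All of this stands and limits the impact. It lets a reader look behind the counts but does not correct them.

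3. **The examples are hypothetical.** Three of the constant-QTcF absolute examples clear their cut-offs by less than 1 ms (450.8, 481.5 and 481.2), and the constant-QTcF change examples need heart-rate rises of 38 to 40 bpm. This stands as a limit on size. The examples show the mechanism and its direction, not a frequency.

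4. **As-reported values match the entry scale.** The 450 ms entry limit is applied to whatever formula the site used. That is a fair reason to keep the site-reported values and the all-methods rows, and the fix keeps both.

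**Conclusion.** The point holds as a cheap improvement of modest impact. SAP 4.8.4 applies common cut-offs to QTcF, QTcB and unspecified-method QTc, states no split and bars conversion. Any Bazett values are therefore binned partly by heart rate, in either direction. At the assumed heart rates and constant QTcF, the effect falls mainly in the 450-480, 481-500 and 31-60 ms rows.

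Two stronger readings are not supported. A reader might infer that the table will overstate QT prolongation. The under-count examples show that it can also hide a rise, and the documents give neither heart rates nor the share of Bazett readings from which a net direction could be worked out. A reader might also infer that heart rate alone will commonly fill the ≥501 and >60 ms rows. In the three tabulated scenarios that needs about 131 bpm or more, and even at the entry limit about 116 bpm for ≥501.

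The number of patients affected cannot be computed from the documents. It is nil if every reported value is QTcF.

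**What to change.** Keep the existing all-methods rows as the overall count, and add to SAP 4.8.4:

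> The absolute and change-from-baseline rows will also be shown by correction method (QTcF, QTcB, unspecified). Each patient is counted once, at the worst value, in the overall rows, and once per method for which the patient has a value, so method rows may sum to more than the overall row. A change whose two values do not carry the same method label is shown under unspecified, under the existing consistent-method assumption.

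Keeping the overall rows matters. Without them, a patient whose ECGs carry different labels could appear in two blocks, and the number of patients with any QTc of 501 ms or more could no longer be read from the table.

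**Optional supplement.** Add a sensitivity row using QTcF = QTcB × (HR/60)^(−1/6), with the heart rate from the same ECG, without replacing the site-reported values. The sentence ruling out conversion would need an exception for this row.

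**Cost.** No new data are needed. The method rows will hold small counts by dose level, but the SAP already provides that "if some dose levels have only a few subjects, then dose levels can be combined into dose ranges". The supplement needs one derived variable. For a QTcB of 450 ms, rounding of QTcB (±0.5 ms) and heart rate (±0.5 bpm) moves the derived QTcF by about 0.8 ms at 100 bpm, 1.1 ms at 60 bpm and 1.4 ms at 45 bpm. It also relies on the recorded heart rate being the one the site used for QTcB, which the documents do not state.
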